| 7.1. Discontinuation of Study Intervention..... | 8 |
| 7.2. Participant Discontinuation/Withdrawal from the Study..... | 8 |
| 7.3. Lost to Follow up..... | 8 |
| 8. Study Assessment and Procedure..... | 8 |
| 8.1 Visit 1 | 8 |
| 8.2 Visit 2 | 9 |
| 8.3 Visit 3 | 9 |
| 8.4 Visit 4 | 10 |

| | |
|--|----|
| 8.5 Visit 5 | 10 |
| 8.6 Visit 6 | 10 |
| 9. Statistical Analysis Overview | 11 |
| 9.1 Primary Efficacy Analysis | 11 |
| 9.2 Reporting | 11 |
| 9.3 Handling of Missing Data | 11 |

1. Synopsis

Protocol Title: A Double-Blinded, Parallel, Vehicle-Controlled Phase 2 Study of SHJ002 Sterile Ophthalmic Solution in Participants with Dry Eye Disease

Brief Title: A study to investigate the efficacy and safety of SHJ002 sterile ophthalmic solution compared with vehicle in participants aged 18 years or older with dry eye disease.

Regulatory Agency Identifier Number(s): NCT05486728

Name of Sponsor: Dreamhawk Vision Biotech Australia Pty Ltd

Investigational Product:

Name: SHJ002 Sterile Ophthalmic Solution

Active Ingredient: SHJ002

Indication: Treatment of signs and symptoms of Dry Eye Disease (DED)

Dose and Administration: SHJ002 Sterile Ophthalmic Solution 0.25%, and vehicle solution, BID, both eyes

Protocol Number: SHJ002-DED2203

Primary Objective: To evaluate the efficacy of SHJ002 ophthalmic solution in improving corneal fluorescein staining scores in participants with Dry Eye Disease (DED).

Secondary Objectives: To assess changes in patient-reported symptom scores using the SANDE and VAS instruments.

Design: Multicenter, double-blinded, randomized, vehicle-controlled, parallel-group Phase 2 trial

Participants: Adults ≥ 18 years old with signs and symptoms of DED in both eyes for ≥ 6 months

Randomization: 1:1 ratio to SHJ002 or vehicle group

Treatment: One drop per eye, twice daily (BID) for 84 days

Sites: Australia, Thailand, Taiwan

2. Introduction

2.1 Rationale:

The purpose of this study is to investigate the efficacy and safety of SHJ002 sterile ophthalmic solution compared to the vehicle in participants with DED.

2.2 Background

Dry eye disease (DED) is a multifactorial disease of the tears and ocular surface that results in symptoms of discomfort, visual disturbance, and tear film instability with potential damage to the ocular surface. It is accompanied by increased osmolarity of the tear film and inflammation of the ocular surface (Nelson, 2017).

Jones et al., 2017 summarizes a host of treatments for DED. These include surgical intervention for lid or other anatomical pathologies, and punctal plugs to treat DED. Other publications highlight thermal pulsation systems, intense pulsed light and meibomian gland probing, some with seemingly long-lasting effects. However, for the most part, treatment of ocular surface disease requires daily or more frequent treatment with tear products (typically over-the-counter) or one of the five U.S. approved pharmacotherapeutic agents. Ocular surface disease is typically a lifetime disease and requires a vigilant patient and eye care professional to treat the disease, both initially and chronically (Novack 2020).

The investigational drug product SHJ002 is a sterile ophthalmic solution, which was originally developed to control myopia progression in pediatric participants. The first-in-human (FIH) Phase-1 study (Study number: SHJ002-CS201) was conducted in a single-center as an open-label, intra-subject, dose-escalation trial in healthy participants aged 10-15 years old. In this FIH study, there was a Stage 1 for dose escalation and a Stage 2 for the highest tolerable dose from the Stage 1 group. A total of 12 participants were enrolled in the Phase-1 study. There were no clinically significant abnormalities or changes in terms of all ophthalmologic evaluations observed during study period. All the participants had completed the study with full compliance without skipping any dosing. There was only one non-study-medication-related treatment emergent adverse events (TEAE). This was punctate keratitis in the non-treated eye that was observed during the study period, and this event was transient and spontaneously resolved before the end of this study.

3. Objectives and Endpoints

The primary objective of this study is to assess the efficacy of SHJ002 sterile ophthalmic solution relative to vehicle

3.1 Primary Endpoint:

- Change from Baseline to Day 84 in Total Corneal Fluorescein Staining (NEI Scale, score range 0–15; higher scores indicate more severe staining)

3.2 Secondary Endpoints:

- Change from Baseline to Day 84 in SANDE score (0–100 scale, higher = worse symptoms)
- Change from Baseline to Day 84 in VAS eye dryness score (0–100 mm, higher = worse discomfort)

4. Study Design

This is a multi-center, double-blinded, randomized, vehicle-controlled, parallel-group trial in adult participants with signs and symptoms of Dry Eye Disease.

Participants who meet the eligibility criteria at Screening will be randomized to receive the treatment with 0.25% SHJ002 ophthalmic solution or vehicle in a 1:1 ratio. SHJ002 ophthalmic solution or vehicle will be administered to each eye twice daily (BID), for 84 days.

This study consists of three periods: a Screening Period of up to 14 days to assess a participant's eligibility, a 1-day Baseline/ randomization period (Day 1) followed by a treatment period of up to 84 days.

Screening Period begins once the participant has provided written informed consent to participate in the study (Visit 1). During this period, participants will be dispensed with the run-in medication (vehicle) for 14 days, along with self-administration instructions. The run-in medication will be administered as the investigational medicinal product (IMP), BID each day. Eligible participants will be thereafter administered with the study treatment (SHJ002), or vehicle bilaterally BID for 12 weeks.

5. Study Population

5.1 Inclusion Criteria:

- Male or female participants 18 years of age or older inclusive, at the time of signing the informed consent.
- Diagnosis of bilateral DED \geq 6 months
- Negative pregnancy test for women of childbearing potential

5.2 Exclusion Criteria:

- Significant ocular surface disease other than DED
- Recent ocular surgery or procedures
- Concurrent use of conflicting topical/systemic therapies

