7.3. Lost to Follow up

A participant will be considered lost to follow-up if the participant repeatedly fails to return for scheduled visits and is unable to be contacted by the study site.

8. Study Assessment and Procedure

8.1 Visit 1

- Obtain written informed consent
- Review Inclusion/exclusion criteria
- Demographics

- Medical and ocular history
- Concomitant medication review
- AE assessment
- SANDE
- Refraction
- BCVA (logMAR)
- Non-invasive lipid layer assessment
- Non-invasive tear break up time (NIBUT)
- Slit lamp biomicroscopy and external eye exam + photography for conjunctival hyperemia
- CFS + photography
- Unanesthetized Schirmer's test
- Intraocular pressure
- Dilated fundoscopy (indirect)
- Urine pregnancy (women of child-bearing potential only)
- Vital signs
- Physical examination
- Clinical laboratory tests

8.2 Visit 2

- Review inclusion/exclusion criteria
- Concomitant medication review
- AE assessment
- SANDE
- Visual Analogue Scale (VAS)
- IP comfort assessment
- BCVA (logMAR)
- Non-invasive lipid layer assessment
- Non-invasive tear break up time (NIBUT)
- Slit lamp biomicroscopy and external eye exam + photography for conjunctival hyperemia
- CFS + photography
- Randomization
- Vital signs

8.3 Visit 3

- Concomitant medication review
- AE assessment
- SANDE
- Visual Analogue Scale (VAS)
- IP comfort assessment
- BCVA (logMAR)
- Non-invasive lipid layer assessment
- Non-invasive tear break up time (NIBUT)
- Slit lamp biomicroscopy/external eye exam + photography for conjunctival hyperemia
- CFS + photography
- Vital signs
- IP return for accountability

8.4 Visit 4

- Concomitant medication review
- AE assessment
- SANDE
- Visual Analogue Scale (VAS)
- IP comfort assessment
- BCVA (logMAR)
- Non-invasive lipid layer assessment
- Non-invasive tear break up time (NIBUT)
- Slit lamp biomicroscopy and external eye exam + photography for conjunctival hyperemia
- CFS + photography
- Urine pregnancy test (women of child-bearing potential only)
- Vital signs

8.5 Visit 5

- Concomitant medication review
- AE assessment
- SANDE
- Visual Analogue Scale (VAS)
- IP comfort assessment
- BCVA (logMAR)
- Non-invasive lipid layer assessment
- Non-invasive tear break up time (NIBUT)
- Slit lamp biomicroscopy and external eye exam + photography for conjunctival hyperemia
- CFS + photography
- Urine pregnancy test (women of child-bearing potential only)
- Vital signs

8.6 Visit 6

- Concomitant medication review
- AE assessment
- SANDE

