- Visual Analogue Scale (VAS)
- IP comfort assessment
- BCVA (logMAR)
- Non-invasive lipid layer assessment
- Non-invasive tear break up time (NIBUT)
- Slit lamp biomicroscopy and external eye exam + photography for conjunctival hyperemia
- CFS + photography
- Intraocular pressure
- Dilated fundoscopy (indirect)
- Urine pregnancy test (women of child-bearing potential only)
- IP return for accountability
- Vital signs
- Clinical laboratory tests

9. Statistical Analysis Overview

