9.1 Primary Efficacy Analysis

Mixed Model for Repeated Measures (MMRM) for change in NEI tCFS score, with baseline, treatment, visit, and treatment-by-visit interaction as covariates.

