9.2 Reporting

Results include LS means, standard error, 95% CI, between-group comparisons with p-values.

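### Does the silence on how two treated eyes become one corneal staining score undermine the primary analysis?

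*Combined protocol and SAP*

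**What the plan says.** The Synopsis enrols adults "with signs and symptoms of DED in both eyes", and section 4 (Study Design) states that "SHJ002 ophthalmic solution or vehicle will be administered to each eye twice daily (BID), for 84 days". Both eyes are therefore diseased and both are treated.

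Section 3.1 gives one primary variable: "Change from Baseline to Day 84 in Total Corneal Fluorescein Staining", scored on the NEI scale from 0 to 15. Sections 8.1 to 8.6 list the assessment at all six visits only as "CFS + photography", with no eye named. Section 9.1 gives the model: "Mixed Model for Repeated Measures (MMRM) for change in NEI tCFS score, with baseline, treatment, visit, and treatment-by-visit interaction as covariates". It has no eye term and does not state the unit of analysis. Section 9.2 adds: "Results include LS means, standard error, 95% CI, between-group comparisons with p-values".

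No section of the supplied text names a study eye, a worse eye or a two-eye average. The statistical part is headed "Statistical Analysis Overview". It gives no sample size, significance level or covariance structure, and section 7.1 refers to a schedule of assessments that is not in the text. A fuller document may hold the rule.

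**The concern.** Two statisticians who follow 3.1 and 9.1 faithfully could build different primary datasets. The 0 to 15 range rules out adding two eyes that are each scored 0 to 15. It still allows a fixed eye, the eye worse at Baseline, the worst eye at each visit, or the mean.

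Three things seem to be at stake. Power depends on the rule. In a borderline trial, one rule may reach p < 0.05 where another does not. The worse-eye rule also makes each arm seem to improve through regression to the mean, and 9.2 reports within-arm LS means. If the rule were picked after unblinding, the false-positive rate would rise as well.

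**Working it through.** **Inputs.** The documents give no sample size, SD, effect, significance level or between-eye correlation, so there is no stated figure to reproduce. Assumed: 50 per arm, two-sided 0.05 (in line with the 95% CI in 9.2), between-eye correlation rho of 0.5 or 0.8, and Baseline to Day 84 correlation r = 0.5. Baseline-adjusted ANCOVA at Day 84 with complete data stands in for the MMRM contrast.

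**1. Validity.** With no true effect (100,000 simulated trials), the fixed eye, the mean and the Baseline-worse eye each reject in 0.049 to 0.051 of trials. A separate simulation (3,000 trials per setting; integer scores bounded at 0 and 15; 30, 50 or 100 per arm; rho 0.5 or 0.7) added the worst eye at each visit. The four rules ranged from 0.043 to 0.059. Each of these rules, once fixed, gives a valid test.

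**2. Power, equal effect in both eyes.** Averaging multiplies the residual variance by (1 + rho)/2. If the mean has 80% power, its standardised effect is 1.960 + 0.842 = 2.802. A single eye then has:
- rho 0.5: 2.802 × √0.75 = 2.427; power Φ(2.427 − 1.960) = 0.68 (simulated 0.679)
- rho 0.8: 2.802 × √0.90 = 2.658; power Φ(2.658 − 1.960) = 0.76 (simulated 0.752)

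The Baseline-worse eye gives 0.678 and 0.752.

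**3. Disagreement on p < 0.05, mean against Baseline-worse eye.**

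| Effect in less-stained eye | rho | Power, mean | Power, worse eye | Disagree |
|---|---|---|---|---|
| 100% | 0.5 | 0.797 | 0.678 | 0.166 |
| 100% | 0.8 | 0.794 | 0.752 | 0.085 |
| 75% | 0.5 | 0.687 | 0.681 | 0.148 |
| 75% | 0.8 | 0.685 | 0.757 | 0.107 |
| 50% | 0.5 | 0.555 | 0.677 | 0.192 |
| 50% | 0.8 | 0.550 | 0.750 | 0.205 |

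Much of this is the power gap itself. In the first row, 0.797 − 0.678 = 0.119 of the 0.166 is the net difference in power. That leaves (0.166 − 0.119)/2 = 0.0235 of trials in which only the worse eye is significant. The direction of the gap reverses when the less-stained eye responds less.

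**4. Within-arm shift, worse-eye rule, no true change.** The expected change is −(1 − r) × SD × √((1 − rho)/π).
- rho 0.5: −0.5 × √(0.5/π) = −0.20 SD
- rho 0.8: −0.5 × √(0.2/π) = −0.13 SD

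At an assumed SD of 3 points this is about −0.6 or −0.4 points. It is the same in both arms, so it cancels in the treatment comparison.

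**5. Choice after unblinding.** The chance that at least one rule is significant under the null is 0.074 (mean or worse eye) or 0.095 (with a fixed eye added) at rho 0.5, and 0.064 or 0.076 at rho 0.8. Nothing in the documents shows that such a choice was made.

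**6. The one harmful reading.** If both eyes entered as independent records, the two-sided error would be 2 × (1 − Φ(1.960/√(1 + rho))).
- rho 0.5: 2 × (1 − Φ(1.600)) = 0.110
- rho 0.8: 2 × (1 − Φ(1.461)) = 0.144

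**The case for a change.** The strongest case for a change is that the omission can be checked without any assumption, that a sentence or two would close it, and that the primary variable cannot be rebuilt from this text alone. The stronger rule depends on how the less-stained eye responds, which argues for stating it. The independent-records reading in step 6 is also not excluded in words, and fixing it in advance would not make it valid.

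All of that stands as a description of the text. It does not show that the planned analysis is unsound. Randomisation is by participant, 3.1 gives one score, and 9.1 is a repeated-measures model over visits with a single baseline term. The ordinary reading is one value per participant per visit. An analyst who did use both eyes would be expected to model their correlation.

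Nor do the documents point to a particular rule. The mean uses both treated eyes and gains power if they respond alike, but it loses power if they do not. It also needs both eyes graded at every visit, which section 8 does not confirm. Section 9.3 treats the data as complete, which suggests they were in hand when the text was written. A rule newly written in at that stage could itself be a post hoc choice.

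**Conclusion.** No change to the plan follows. The gap is real, but it is one that analysts fill sensibly, and the choice between the sensible rules is a fair trade-off. Each participant-level rule keeps the nominal level if fixed before unblinding, and the worse-eye shift of 0.13 to 0.20 SD cancels between arms.

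The rules can differ on whether p < 0.05, in about 8.5% to 20.5% of simulated trials for the mean against the Baseline-worse eye. That is significant against not significant. It does not mean benefit against harm. With equal effects and 50 per arm, estimates from those two rules differed in sign in under 1% of trials, and they were never both significant in opposite directions.

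These sizes rest on assumed sample size, effect, SD and correlations, so they illustrate the issue and do not estimate this trial's risk. With equal effects, disagreement falls to about 6% at rho 0.9. It stays near 22% to 23% at high correlation if the less-stained eye gets half the effect. The conclusion would change only if both eyes had been analysed as independent records, or if the rule had been chosen after unblinding. The documents show neither.

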5.3. Lifestyle Considerations

Alcohol and/or drug abuse that, in the opinion of the Investigator, may interfere with study compliance, outcome measures, safety parameters, and the general medical conditions of the participant; hence, alcohol and drug abuse should refrain within 12 months prior to Visit 1/Screening.

5.3.1. Meals and Dietary Restrictions

Not applicable

5.3.2. Caffeine, Alcohol, and Tobacco

Not applicable

5.3.3. Activity

Participants will abstain from strenuous exercise for 48 hours before each blood collection for clinical laboratory tests (Screening and Visit 6). Participants may undertake in light recreational activities during studies (e.g., watching television, reading).

5.3.4. Other Restrictions

Not applicable.

5.4. Screen Failures

A screen failure occurs when a participant who has consented to participate in the clinical study is not subsequently assigned to study intervention/entered in the study. A minimal set of screen failure information is required to ensure transparent reporting of screen failure participants to meet the CONSORT publishing requirements and to respond to queries from regulatory authorities. Minimal information includes demography, screen failure details, eligibility criteria, and any SAE. Individuals who do not meet the criteria for participation in this study (screen failure) may be rescreened. Rescreened participant should be assigned a new participant number for every screening/rescreening event.

5.5. Criteria for Temporarily Delaying

Not applicable

6. Study Intervention

Study interventions are all pre-specified, investigational, and non-investigational medicinal products, intended to be administered to the study participants during the study conduct.

6.1 Study Intervention(s) Administered

Participants will be randomly assigned to:

- 0.25% SHJ002 Sterile Ophthalmic Solution
- Vehicle Sterile Ophthalmic Solution without active pharmaceutical ingredient (API)

6.1.1. Study Drug

SHJ002 Sterile Ophthalmic Solution is formulated as a sterile, preservative-free solution at pH 7.0 for topical ophthalmic administration.

6.1.2. Vehicle

The vehicle used in this trial is an artificial tear solution manufactured by the sponsor that mimics the osmolality and natural pH of human tears.

6.2. Preparation, Handling, Storage, and Accountability

The Drug Product is supplied in a single use LDPE vial. Drug products are stored at 2~8°C under ambient humidity until dispensation to participant. Participant may keep drug product either refrigerated (2~8°C) or at room temperature (25±2°C).

IMP kit shipment records will be verified, and accountability performed by comparing the shipment inventory sheet to the actual quantity received at the site. In addition, receipt of IMP

will be confirmed by the study monitor. Accurate records of receipt and disposition of the IMP must be maintained by the Investigator or his/her designee.

At the end of the study and after the monitor has verified kit accountability, all IMP (used or unused) is to be returned to the Sponsor or destroyed at the site and documented per the site's standard process.

6.3. Assignment to Study Intervention

Participants will be randomized in a 1:1 ratio to 0.25% SHJ002 or vehicle in parallel groups.

7. Discontinuation of Study Intervention and Participant Discontinuation/Withdrawal

7.1. Discontinuation of Study Intervention

In rare instances, it may be necessary for a participant to permanently discontinue the study intervention. If the study intervention is permanently discontinued, the participant should, if at all possible, remain in the study to be evaluated. See the SoA for data to be collected at the time of discontinuation of study intervention and follow-up and for any further evaluations that need to be completed.

7.2. Participant Discontinuation/Withdrawal from the Study

A participant may withdraw from the study at any time at the participant's own request for any reason (or without providing any reason).

A participant may be withdrawn at any time at the discretion of the investigator for safety, behavioral, or compliance reasons.

At the time of discontinuing from the study, if possible, an early discontinuation visit should be conducted. Data to be collected at the time of study discontinuation and follow-up and for any further evaluations that need to be completed.

The participant will be permanently discontinued from the study intervention and the study at that time.

If the participant withdraws consent for disclosure of future information, the sponsor may retain and continue to use any data collected before such a withdrawal of consent.

If a participant withdraws from the study, the participant may request destruction of any samples taken and not tested, and the investigator must document this in the site study records.

7.3. Lost to Follow up

A participant will be considered lost to follow-up if the participant repeatedly fails to return for scheduled visits and is unable to be contacted by the study site.

8. Study Assessment and Procedure

8.1 Visit 1

- Obtain written informed consent
- Review Inclusion/exclusion criteria
- Demographics

- Medical and ocular history
- Concomitant medication review
- AE assessment
- SANDE
- Refraction
- BCVA (logMAR)
- Non-invasive lipid layer assessment
- Non-invasive tear break up time (NIBUT)
- Slit lamp biomicroscopy and external eye exam + photography for conjunctival hyperemia
- CFS + photography
- Unanesthetized Schirmer's test
- Intraocular pressure
- Dilated fundoscopy (indirect)
- Urine pregnancy (women of child-bearing potential only)
- Vital signs
- Physical examination
- Clinical laboratory tests

8.2 Visit 2

- Review inclusion/exclusion criteria
- Concomitant medication review
- AE assessment
- SANDE
- Visual Analogue Scale (VAS)
- IP comfort assessment
- BCVA (logMAR)
- Non-invasive lipid layer assessment
- Non-invasive tear break up time (NIBUT)
- Slit lamp biomicroscopy and external eye exam + photography for conjunctival hyperemia
- CFS + photography
- Randomization
- Vital signs

8.3 Visit 3

- Concomitant medication review
- AE assessment
- SANDE
- Visual Analogue Scale (VAS)
- IP comfort assessment
- BCVA (logMAR)
- Non-invasive lipid layer assessment
- Non-invasive tear break up time (NIBUT)
- Slit lamp biomicroscopy/external eye exam + photography for conjunctival hyperemia
- CFS + photography
- Vital signs
- IP return for accountability

8.4 Visit 4

- Concomitant medication review
- AE assessment
- SANDE
- Visual Analogue Scale (VAS)
- IP comfort assessment
- BCVA (logMAR)
- Non-invasive lipid layer assessment
- Non-invasive tear break up time (NIBUT)
- Slit lamp biomicroscopy and external eye exam + photography for conjunctival hyperemia
- CFS + photography
- Urine pregnancy test (women of child-bearing potential only)
- Vital signs

8.5 Visit 5

- Concomitant medication review
- AE assessment
- SANDE
- Visual Analogue Scale (VAS)
- IP comfort assessment
- BCVA (logMAR)
- Non-invasive lipid layer assessment
- Non-invasive tear break up time (NIBUT)
- Slit lamp biomicroscopy and external eye exam + photography for conjunctival hyperemia
- CFS + photography
- Urine pregnancy test (women of child-bearing potential only)
- Vital signs

8.6 Visit 6

- Concomitant medication review
- AE assessment
- SANDE
- Visual Analogue Scale (VAS)
- IP comfort assessment
- BCVA (logMAR)
- Non-invasive lipid layer assessment
- Non-invasive tear break up time (NIBUT)
- Slit lamp biomicroscopy and external eye exam + photography for conjunctival hyperemia
- CFS + photography
- Intraocular pressure
- Dilated fundoscopy (indirect)
- Urine pregnancy test (women of child-bearing potential only)
- IP return for accountability
- Vital signs
- Clinical laboratory tests

9. Statistical Analysis Overview

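### On the Section 8 visit lists, no pregnancy test falls between the start of the 14-day vehicle run-in and randomisation, so SHJ002 can be started on a negative result up to about 14 days old

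*Combined protocol and SAP*

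**What the plan says.** All references are to the combined protocol and SAP.

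- **Eligibility (Section 5.1).** One of the three inclusion criteria is "Negative pregnancy test for women of childbearing potential". No window relative to randomisation or first dose is attached.
- **Timing (Section 4).** Visit 1 opens "a Screening Period of up to 14 days to assess a participant's eligibility". On the run-in: "During this period, participants will be dispensed with the run-in medication (vehicle) for 14 days". Day 1 is baseline and randomisation. Then: "Eligible participants will be thereafter administered with the study treatment (SHJ002), or vehicle bilaterally BID for 12 weeks".
- **Visit lists (Section 8).** A urine pregnancy test for women of child-bearing potential is listed in 8.1 (Visit 1), 8.4, 8.5 and 8.6 (Visits 4 to 6). It is absent from 8.2 (Visit 2) and 8.3 (Visit 3). Randomisation appears only in 8.2.
- **Eligibility re-check.** The entry "Review Inclusion/exclusion criteria" stands in the Visit 1 list and, apart from a capital letter, again in the Visit 2 list.
- **Allocation (Section 6.3).** "Participants will be randomized in a 1:1 ratio to 0.25% SHJ002 or vehicle in parallel groups".
- **Earlier human data (Section 2.2).** The only human study described is a "dose-escalation trial in healthy participants aged 10-15 years old". Its size: "A total of 12 participants were enrolled in the Phase-1 study".

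**The concern.** During the run-in every participant receives vehicle, which Section 6.1 describes as lacking the active ingredient. The single listed pre-randomisation test therefore guards entry to the vehicle phase. First exposure to SHJ002 comes after Visit 2, where no test is listed.

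Visit 2 is the last listed visit before randomised drug starts. A test there can prevent exposure of a pregnancy that is detectable by then. The tests at Visits 4, 5 and 6 can only find a pregnancy after exposure, under twice-daily dosing in both eyes.

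The supplied text gives no reproductive-safety information, and the one human study it describes was in healthy 10- to 15-year-olds. The size of the hazard is therefore unknown. What is at stake is participant safety. The estimate of the treatment effect on corneal staining is not.

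**Working it through.** The plan states no figure of its own on this point, so there is none to reproduce. The check sets the visit lists side by side and then works out what a Visit 2 test could and could not detect.

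**Step 1. Where the test is listed (Sections 8.1 to 8.6).**

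| Visit | Urine pregnancy test listed | Place in the trial |
|---|---|---|
| 1 | Yes | Screening, start of run-in |
| 2 | No | Randomisation |
| 3 | No | On treatment |
| 4 | Yes | On treatment |
| 5 | Yes | On treatment |
| 6 | Yes | On treatment |

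Of 4 listed tests, 1 is before the run-in, 0 are at randomisation and 3 are on treatment.

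**Step 2. Age of the result at the first randomised dose.** The screening maximum and the run-in length in Section 4 are both 14 days. For a participant who completes the run-in, the Visit 1 result is about 14 days old at Visit 2. A shorter interval is possible, because screening has a maximum and no minimum.

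**Step 3. Does the Visit 2 eligibility review force a new test?** The criterion has no time window, and the 13 entries in the Visit 2 list include no pregnancy test. A site following the text could count the Visit 1 result as meeting the criterion.

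**Step 4. What a Visit 2 test would add.** Let d be the days from conception until a urine test turns positive. The documents give no value; I assume a range of 7 to 14 days. Take a full 14-day run-in.

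- The Visit 1 test misses conceptions in the d days before Visit 1.
- The Visit 2 test would detect conceptions up to 14 − d days into the run-in, and would miss those in its last d days.
- Conception dates undetected at first dose therefore span 14 + d days without the Visit 2 test, and d days with it. The difference is always 14 days: d days before Visit 1 plus 14 − d days of the run-in.

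| d (assumed) | Undetected span now (14 + d) | Undetected span with Visit 2 test (d) | Gained before Visit 1 (d) | Gained within run-in (14 − d) |
|---|---|---|---|---|
| 7 days | 21 days | 7 days | 7 days | 7 days |
| 10 days | 24 days | 10 days | 10 days | 4 days |
| 14 days | 28 days | 14 days | 14 days | 0 days |

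These are spans of conception dates, not counts of women. At d = 7 the gain is split equally between the period before Visit 1 and the run-in. At d = 14 all of it lies before Visit 1.

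**Step 5. Allocation.** Under 1:1 randomisation, 1/(1 + 1) = 50% of affected women would be expected to receive SHJ002. The rest would receive vehicle and have no exposure to the active ingredient.

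**Not computable.** The number of women affected cannot be stated, because no sample size is given. The time from first dose to the next listed test cannot be stated either, because Visit 4 has no study day.

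**The case against.** **The lists are condensed.** None of the six visits lists drug dispensing, although Section 4 says run-in medication is dispensed. Return of study drug appears only at Visits 3 and 6. The early discontinuation visit in Section 7.2 has no list. Section 7.1 refers to an SoA that was not supplied and may already show a Visit 2 test. This objection stands in part. A reader might infer that the trial does not test at randomisation, and the documents do not support that. They show only that Section 8.2 omits the test. The omission is still worth correcting: Section 8 includes or leaves out this item visit by visit, and if the SoA has the test then Section 8.2 disagrees with it.

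**Section 5 is equally brief.** Other criteria, such as recent ocular surgery, also lack a window. The missing window may reflect summary style and does not show a decision to accept an old result. That is fair. No rule in the documents is broken, and a screening test within 14 days of dosing followed by three on-treatment tests is a design choice.

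**Eligibility is reviewed again at Visit 2.** This is a real but partial safeguard. The text neither requires a new test nor says outright that the Visit 1 result suffices. The second is my reading of a criterion without a window.

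**The fix does little for conceptions during the run-in.** This stands. It is tempting to say that a same-day result would prevent exposure of run-in conceptions generally. Step 4 shows otherwise: only conceptions in the first 0 to 7 days of the run-in would be caught, under the assumed lag. Much or all of the gain is in pregnancies too early to show at Visit 1, which are also worth detecting.

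**No consequence is quantified.** Also true. Reproductive-safety data and contraception rules may sit in documents not supplied. This limits the priority of the point but does not remove it, given the small cost.

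**Conclusion.** The point holds as a cheap, modest safety improvement. On the Section 8 lists, the only pregnancy test before randomisation is at Visit 1. With no recency window in Section 5.1, SHJ002 can be started on a negative result up to about 14 days old. A Visit 2 test would make the result same-day at randomisation and shorten the span of undetected conception dates by 14 days, from 21–28 days to 7–14 days.

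This rests on a full 14-day run-in, on Section 8 reflecting what sites do, and on the assumed detection lag of 7 to 14 days. A same-day negative would still not exclude a very early pregnancy: conceptions in the last 7 to 14 days of the run-in would be missed. The documents do not support reading this as a breach of the protocol, a demonstrated harm or a threat to the primary analysis.

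**What to change.** 1. In Section 8.2, add the urine pregnancy test entry already used in Sections 8.4 to 8.6, placed before randomisation.
2. State that the result must be negative before randomisation.
3. Align the SoA. If it already has a Visit 2 test, only Section 8.2 needs correcting.

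The cost is one extra urine test per woman of child-bearing potential (4 + 1 = 5 listed tests), at an existing visit and with a test the trial already uses. An occasional participant will become a screen failure after completing the run-in. No visit is added and the primary analysis does not change. The wait from Visit 2 to the next listed test at Visit 4 also stays as it is.
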